8.1.2 Pregnancy reporting

Pregnancies

To ensure subject safety, each pregnancy occurring after signing the informed consent must be reported by the investigator to the sponsor. The pregnancy should be followed up to determine outcome, including spontaneous or voluntary termination, details of the birth, and the presence or absence of any birth defects, congenital abnormalities, or maternal and/or newborn complications. Pregnancy follow-up should include an assessment of the possible relationship to the study medication/supplement of any pregnancy outcome. Any SAE experienced during pregnancy must be reported.

8.1.3 Executive Committee

The Executive Committee (EC) will play an active role in providing scientific guidance and advice to the sponsor related to the design, conduct, results analysis, and publication strategy for the SPORT study. The EC will be composed of members who are experts in preventive cardiology with relevant clinical trial methodological expertise. Meeting frequency, membership, and specific responsibilities will be further described in the EC Charter.

9 Data collection and database management

9.1 Data collection

Designated investigator staff will enter the data required by the protocol into the Electronic Case Report Forms (eCRF) within the REDCap Cloud database. The eCRFs have been built using fully validated secure web-enabled software that conforms to 21 CFR Part 11 requirements.

The investigator/designee is responsible for assuring that the data entered into eCRF is complete, accurate, and that entry and updates are performed in a timely manner. The Investigator must certify that the data entered are complete and accurate.

After final database lock, the investigator will receive copies of the subject data for archiving at the investigational site.

All data should be recorded, handled and stored in a way that allows its accurate reporting, interpretation and verification.

9.2 Safety monitoring

The investigator must maintain source documents for each subject in the study, consisting of case and visit notes (hospital or clinic medical records) which may include demographic and medical information, laboratory data, and the results of any other tests or assessments. All information on eCRFs must be traceable to these source documents in the subject's file. The investigator must also keep the original informed consent form signed by the subject (a signed copy is given to the subject).

A Medical Monitor will review safety data for the study as specified in the Medical Monitor Charter.

10 Data analysis and statistical methods

10.1 Analysis sets

The following analysis populations will be defined for statistical analysis:

The **full analysis set (FAS)** consists of all enrolled patients. Efficacy variables will be analyzed based on the FAS as the primary population.

The **safety analysis set (SAS)** consists of all patients who received at least one dose of study medication/supplement. The safety population will be used for the analyses of safety variables.

10.2 Subject disposition

The number of patients screened will be presented by study group and overall for the screened set. In addition, the reasons of screen failures will be provided for screened set as well. The number and percentage of patients who completed the study, who discontinued the study and the reason for discontinuation will be presented for each study group and all patients. The frequency (%) of patients with major protocol deviations will be presented in separate tables.

10.3 Subject demographics and baseline characteristics

All demographic and baseline characteristics summaries will be based on the FAS. They will be presented in summary tables by study group. Continuous data will be summarized by descriptive statistics, and categorical data will be summarized by frequency distributions. Finally, the number of enrolled patients by site will be presented descriptively.

10.4 Study evaluations

10.4.1 Study medication/supplement

The duration of the study medication/supplement use will be computed as the time from the first dose to the patient's study completion visit during the study close-out period.

The duration of the study medication/supplement use will be summarized for the full analysis set and safety set by study group descriptively including by duration categories.

The safety set will be used for the above analyses unless otherwise specified.

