Hs-CRP	X	X
CMP, LDL-C, TC, HDL-C, and TG ^{c,d}	X	X
Pregnancy test ^a	X	
Study medication/supplement dispensed ⁱ	X	
Adverse events		X
Study medication/supplement adherence ^e		X

^a Females of child-bearing potential only, urine or serum at investigator's discretion.

^b The baseline (0) and 28 Day visit may be completed remotely. Consent will be obtained prior to completion of the baseline visit and may be completed remotely in accordance with Cleveland Clinic guidelines

^c Fasting lipid panel and complete metabolic panel should be drawn at a Cleveland Clinic lab facility. Patients should fast for approximately 8 hours.

^d Recently acquired lipid and complete metabolic panel labs may be used in place of a Day 0 lab draw if acquired within 4 weeks of screening at a Cleveland Clinic lab.

^e Study medication/supplement adherence will be assessed with a pill count. The bottle will be returned to the study site to retain until the end of study.

^f If enrolled for over 14 days and the patient discontinues study medication/supplement perform Day 28 lab work (ITT principle).

^g Historical documented height and weight may be used. Weight to be within the last 3 months. Subject reported is acceptable.

^h Randomization and eligibility confirmation may occur on different days from baseline pending lab results

ⁱ Study medication/supplement will be dispensed by the investigational pharmacy for in person visits to study personnel or shipped to the subjects by the investigational pharmacy following randomization.

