7.1 Discontinuation

7.1.1 Discontinuation of study medication/supplement

Discontinuation of study medication/supplement for a subject occurs when the study medication/supplement is stopped earlier than the protocol planned duration, and can be initiated by either the subject or the investigator.

The investigator must discontinue study medication/supplement for a given subject if, he/she believes that continuation would negatively impact the subject's well-being. After study medication/supplement discontinuation, the patient should remain in the study, unless he/she withdraws consent, preferably in writing.

Study medication/supplement must be discontinued under the following circumstances:

- Subject decision
- Pregnancy
- Any situation in which study participation might result in a safety risk to the subject
- Any laboratory abnormalities that in the judgment of the investigator prevents the subject from continuing study medication/supplement administration

If discontinuation of study medication/supplement occurs, the investigator should make a reasonable effort to understand the primary reason for the subject's premature discontinuation of study medication/supplement and record this information.

Subjects who discontinue study medication/supplement or who decide they do not wish to participate in the study further should NOT be considered withdrawn from the study UNLESS they withdraw their consent. If discontinuation occurs after Day 14, study personnel should attempt to obtain Day 28 labs as close as possible to last dose of study medication/supplement taken.

Where possible, they should return for the Day 28 assessments indicated in the assessment schedule. If they fail to return for these assessments for unknown reasons, every effort (e.g. telephone, e-mail, and letter) should be made to contact the subject/pre-designated contact per institutional guidelines to collect as much data as possible according to the visit schedule.

Patient's vital status can also be verified by the study site upon contact with patient's primary care physician or other sources according to local rules and regulations.

After study medication/supplement discontinuation, at a minimum, in the abbreviated visit, the following data should be collected either during an in person visit or via telephone/email contact:

- new / concomitant treatments
- adverse events/Serious Adverse Events

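### Duration of product use is measured to the final visit, not the last dose, so the descriptive duration summary overstates use for people who stop early and stay in the study

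*Protocol*

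**What the plan says.** Protocol 10.4.1 fixes both ends of the exposure interval: "The duration of the study medication/supplement use will be computed as the time from the first dose to the patient's study completion visit". It makes no exception for people who stop product early. The result is to be "summarized for the full analysis set and safety set by study group descriptively including by duration categories".

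Protocol 7.1.1 separates stopping product from leaving the trial. Discontinuation of product "occurs when the study medication/supplement is stopped earlier than the protocol planned duration". What follows is also stated: "After study medication/supplement discontinuation, the patient should remain in the study, unless he/she withdraws consent, preferably in writing". On the final visit: "Where possible, they should return for the Day 28 assessments indicated in the assessment schedule". For stops after Day 14 there is a further instruction: "study personnel should attempt to obtain Day 28 labs as close as possible to last dose of study medication/supplement taken". Footnote f of the assessment schedule likewise keeps the Day 28 lab work for anyone who stops after more than 14 days in the study.

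The SAP contains no definition of duration of use. Its sections 6.4 and 7.5 cover pill-count adherence, restricted to people with at least 24 days of follow-up and reported in percentage categories.

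**The concern.** A variable labelled duration of use should end when use ends. This one ends at a visit that people are asked to attend whether or not they are still taking product. For anyone who takes product up to the visit the two dates coincide and the rule does no harm. For anyone who stops early and attends, every off-product day before the visit is counted as a day of use.

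What is at stake is the accuracy of one planned description: how long each of the eight groups took its product, as a summary statistic and by duration category. The categories suffer most, because an early stopper who attends at Day 28 moves into the full-duration category.

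**Working it through.** The plan states no duration figure, stopping rate or person-time, so there is nothing to reproduce. The check applies the rule as written to example patients and compares it with duration to last dose.

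**Inputs**
- Day 1 is the first day of product (Protocol 4.3.5; SAP 6.3.1.2).
- Planned use is 4 weeks, or 28 days (Protocol 3).
- The final visit falls on Days 24 to 32 (assessment schedule, Day 28 ±4 days; SAP 6.4).
- Last-dose days 7, 15 and 21 are assumptions chosen for illustration.

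**Formulas**, with V the visit day, L the last-dose day, and days counted inclusively from Day 1:
- Duration under the rule = V.
- Duration to last dose = L.
- Overstatement = V / L.
- Pill-count adherence (SAP 6.4), if every dose was taken until stopping and all remaining pills were returned = L / V. The number of pills per day cancels, so this is the same for every product.

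| Last dose | Quantity | Visit Day 24 | Visit Day 28 | Visit Day 32 |
|---|---|---|---|---|
| Day 7 | V / L | 24/7 = 3.43 | 28/7 = 4.00 | 32/7 = 4.57 |
| Day 7 | Adherence | 29% | 25% | 22% |
| Day 15 | V / L | 24/15 = 1.60 | 28/15 = 1.87 | 32/15 = 2.13 |
| Day 15 | Adherence | 62.5% | 54% | 47% |
| Day 21 | V / L | 24/21 = 1.14 | 28/21 = 1.33 | 32/21 = 1.52 |
| Day 21 | Adherence | 88% | 75% | 66% |

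With a Day 28 visit, the Day 7 stopper is recorded with 28 days of use and 25% adherence. The two planned descriptions of the same person disagree.

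**Group mean.** Suppose a fraction f of a group stops at day L, everyone else has 28 days, and all attend at Day 28. The rule then reports 28.0 days. The mean to last dose is 28 − f × (28 − L):
- f = 5%, L = 15: 28 − 0.05 × 13 = 27.35 days; the rule is 2.4% too long (28/27.35 = 1.024).
- f = 10%, L = 7: 28 − 0.10 × 21 = 25.9 days; 8.1% too long.
- f = 20%, L = 7: 28 − 0.20 × 21 = 23.8 days; 17.6% too long.

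**The Day 14 qualifier.** The Day 15 and Day 21 rows assume that the completion visit takes place at about Day 28. Section 7.1.1 asks for earlier labs in these people. If that draw is the completion visit, V is close to L and most of the overstatement goes. Section 7.2 defines study completion for the trial as a whole, and nothing says whether an early draw is a patient's completion visit. The Day 7 row has no such qualifier, because the early-draw instruction covers only stops after Day 14.

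**The case against.** The strongest case on the other side is that little depends on this variable and that other outputs show stopping.

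A reader might infer that differences between groups in stopping would be hidden. The documents do not support that. A person recorded with about 28 days of use has enough follow-up to enter the adherence calculation. On the assumptions above, someone who stops on Day 15 and attends at Day 28 falls in the 50–70% adherence category, below the 80% threshold, and so outside the per-protocol set (SAP 4.3). Adverse-event listings record withdrawal of product as an action taken (SAP 9.1), and the safety monitoring reports may include discontinuations due to adverse events (SAP 10). These sources are partial. Adherence is a percentage, not a duration, and leaves out anyone with under 24 days of follow-up. The listings show only stops tied to an event. The disposition table counts people who left the study, which under 7.1.1 need not include those who only stopped product.

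A reader might also infer that adverse events would be judged against the wrong exposure. No planned safety analysis has a person-time denominator. Protocol 10.6.1 and SAP 9.1 count subjects and events by group, without formal tests. Nor is there any route from this variable into the LDL-C results.

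Two further points stand. Any figure for a stop after Day 14 is an upper reading, because of the early-draw instruction. And the SAP plans no duration table, so it is open whether the Protocol 10.4.1 summary will be produced at all.

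None of this makes the definition correct. It limits what the error can affect.

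**Conclusion.** The definition is wrong as written: it measures time from first dose to the final visit and calls it use. For someone whose last dose is Day 7, the recorded duration is 3.4 to 4.6 times actual use across the visit window, and 4.0 times with a Day 28 visit. For later stops the ratio is smaller, and it may nearly vanish if the early lab draw counts as the completion visit. The effect on a group mean depends on a stopping rate that the documents do not give; in the three scenarios shown it runs from 2.4% to 17.6%.

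The conclusion rests on early stoppers attending the final visit, as 7.1.1 asks. Severity is minor: one descriptive summary and its categories are affected, and no efficacy or safety inference uses them.

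**What to change.** In Protocol 10.4.1, define duration of use as date of last dose minus date of first dose plus 1. Report time from first dose to the final visit separately, labelled as follow-up. If the duration table is to be produced, put the same definition in the SAP, most naturally in section 7.5, so that it sits beside the adherence categories and the two can be read together.

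The cost is a sentence or two in each document. The one practical requirement is the date of last dose. Protocol 7.1.1 already relies on knowing it to time the labs after a stop later than Day 14, but the assessment schedule does not list it, so confirm that the eCRF captures it for everyone and add the field if it does not.

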10.4.2 Prior and concomitant therapies

Prior or concomitant medication/supplements will be summarized for the safety set in separate tabulations based on a predetermined list of medication/supplements. Prior medication/supplement are defined as any medication/supplement a subject was taking prior to randomization in the study. Concomitant medication/supplements will include any medication/supplements taken during the study period.

10.5 Analysis of the primary endpoint

To control the overall alpha of the study, the primary endpoint will be evaluated hierarchically. Each comparison to rosuvastatin will use an alpha of 0.05. Once a comparison is not met (2-sided p-value ≥ 0.05) all subsequent comparisons will be considered exploratory with nominal p-values. The change in LDL-C for rosuvastatin will be compared with the other 7 study groups using ANCOVA in a hierarchical fashion in the following order:

- Rosuvastatin 5 mg compared with the following:
 1. Placebo (identical to rosuvastatin 5mg)
 2. Fish oil (Nature Made™ 2 soft gels / day)
 3. Cinnamon (1200mg, 2 capsules / day)
 4. Garlique™ (1 tablet / day)
 5. Turmeric (Bio Schwartz Turmeric Curcumin, 1500mg, 3 capsules / day)
 6. Plant sterol (Nature Made CholestOff™ Plus, 2 soft gels 2x / day)
 7. Red yeast rice (Arazo Nutrition, Red Yeast Rice, 1200mg, 2 capsules / day)

If the percent change in LDL has a non-normal distribution (graphically assessed), median values will be used to summarize the endpoints and compared with a non-parametric test. At a minimum, adjustments for baseline LDL and age will be used in summarizing the endpoints. Other adjustments may be warranted if differences in factors across study groups are statistically significant. The primary endpoint will be analyzed in the FAS.

10.6 Analysis of secondary endpoints

The following secondary endpoints will be analyzed in the FAS:

- Percent change in high sensitivity C reactive protein (hsCRP) for each study group compared with rosuvastatin 5 mg
- The percent changes in HDL-C, total cholesterol, and triglycerides for each study group compared with rosuvastatin 5 mg

-
- The percent changes in HDL-C, total cholesterol, and triglycerides for each study group compared with placebo

The comparisons of each study group to placebo will utilize placebo-subtracted changes from baseline. Percent change from baseline for each study group and placebo will first be calculated. The difference found in the placebo arm will then be subtracted from each study group. The mean and 95% confidence intervals will be used to summarize the effect of each study group.

No hierarchical testing of the secondary endpoints will be conducted. Since the study was not powered to test secondary endpoints, all testing and p-values will be considered exploratory. No adjustments will be made for multiplicity.

10.6.1 Adverse events

All information obtained on adverse events will be summarized by study group. A subject with multiple adverse events of the same type is only counted once towards the total of that event. Serious adverse event and deaths resulting from an adverse events will be tabulated. All adverse events, deaths and serious adverse events will be provided in patient listings.

11 Ethical considerations and administrative procedures

11.1 Regulatory and ethical compliance

This clinical study was designed and shall be implemented, executed and reported in accordance with the ICH Harmonized Tripartite Guidelines for Good Clinical Practice, with applicable local regulations (US CFR 21), and with the ethical principles laid down in the Declaration of Helsinki.

## **1. Introduction**

The purpose of this Statistical Analysis Plan (SAP) is to provide a description of the statistical methods to be implemented for the analysis of data from the study with IND Number: 154728. The SAP will be finalized prior to database lock. Any deviations from the SAP after database lock will be documented in the final Clinical Study Report (CSR).

## **2. Objectives and Endpoints**

### **2.1. Primary Objective**

The primary objective of this study is to compare the low density lipoprotein cholesterol (LDL-C) lowering of rosuvastatin with the effect of six commonly-used nonprescription dietary supplements promoted for cholesterol health.

### **2.2. Secondary Objective**

The secondary objective of this study is to assess the effect of each supplement on inflammatory markers compared with rosuvastatin 5 mg.

### **2.3. Primary Endpoint**

The percent change in LDL-C for rosuvastatin 5 mg compared with each dietary supplement after 4 weeks of treatment

### **2.4. Secondary Endpoints**

The secondary endpoints of this study are:

- The percent change in LDL-C for rosuvastatin 5 mg and each dietary supplement compared with placebo after 4 weeks.
- The percent change in high sensitivity C reactive protein (hsCRP) for rosuvastatin 5 mg and each dietary supplement compared with placebo after 4 weeks.
- The percent change in HDL-C, total cholesterol, and triglycerides for each supplement compared with rosuvastatin.
- The percent change in HDL-C, total cholesterol, and triglycerides for each supplement compared with placebo.

## **3. Study Design**

SPORT is a randomized, single blind study design used to evaluate rosuvastatin 5 mg. vs. placebo and 6 commercially available over the counter supplements in a hierarchical testing order. Each participant will take study medication/supplement for a total of 4 weeks. Eight groups will be studied, rosuvastatin 5 mg compared with each of the following:

1. Placebo (visually similar to rosuvastatin 5mg)
2. Fish oil (Nature Made™ 2 soft gels / day)

3. Cinnamon (1200mg, 2 capsules / day)
4. Garlique™ (1 tablet / day)
5. Turmeric (Bio Schwartz Turmeric Curcumin, 1500mg, 3 capsules / day)
6. Plant sterol (Nature Made CholestOff™ Plus, 2 soft gels 2x / day)
7. Red yeast rice (Arazo Nutrition, Red Yeast Rice, 1200mg, 2 capsules / day)

### **3.1. Randomization**

Randomization will occur using REDCap Cloud electronic database platform. Study medication/supplement will be dispensed by the investigational pharmacy in a blinded fashion for in person visits to study personnel or shipped to the subjects by the investigational pharmacy following randomization. Day 1 of the study is the first day that subjects start study medication/supplement. In the event that study medication/supplement is shipped to subjects, study personnel will verify the start of study medication/supplement (Day1) for medication/supplement accountability.

The study medication/supplement will be supplied from commercially available products and administered according to the package insert. The rosuvastatin 5mg and placebo will be provided by Astra Zeneca. The over the counter supplements will be purchased and due to documented history of supplement tainting, supplements may be tested for unlabeled enhancing impurities retrospectively if deemed necessary per data findings. If we observe > 15% lowering in LDL cholesterol, we will test for impurities.

### **3.2. Blinding**

Subjects, investigator staff, persons performing the assessments, and the clinical trial team will be blinded to assigned study group. Baseline laboratory values will not be blinded to the subjects, investigator staff, and the clinical team. Additional lipid labs will be prohibited for the 4 week participation period. The Day 28 labs will not be blinded.

It is expected that the need for unblinding of a patient's study group will be extremely rare. Every effort should be made to preserve the blind unless there is a compelling reason that knowledge of the specific treatment would alter the medical care of the patient.

